3.3.4 Background Therapy Emollient Use

Subjects are to use a protocol-permitted, non-urea-containing emollient on lesional and nonlesional skin daily for at least 1 week before Day 1 and agree to continue using that same emollient daily at the same frequency (ideally once or twice daily) throughout the study. Subjects will record emollient use in a daily diary throughout the study. Every

effort should be made to keep the same emollient throughout the study for the same body region.

Subjects will delay emollient use on the days of study visits until after study procedures are completed.

3.3.5 *Rescue Medications*

New concomitant medications and procedures for treatment of AD are prohibited during the study. If a patient requires treatment with a new medication or procedure due to intolerable AD symptoms, study drug should be discontinued. Whenever possible, subjects should remain in the study and complete the remaining study visits and assessments even when study drug has been discontinued.

3.4 Pharmacodynamic and Safety Variables

3.4.1 *Pharmacokinetic Variables*

[figure not shown]
Blood sampling will be collected predose (as applicable) at Visit 2 (Day 1), and each visit thereafter to analyze trough EP262 concentrations. The EP262 metabolite profile may also be analyzed from these trough samples.

[figure not shown]
3.4.2 *Pharmacodynamic Variables*

[figure not shown]
Pharmacodynamic assessments

[figure not shown]

[figure not shown]
be taken of the area of worst lesional involvement at Visit 2 (Day 1) and of the same area at Visit 3 (Week 3), Visit 4 (Week 6), and Visit 5 (Follow-Up). Photographs will also be taken of areas selected for skin swabs, skin tape strips application, and biopsies before these procedures are conducted.

[figure not shown]

3.4.3 Baseline Characterization

A blood sample will be collected at Visit 2 (Day 1) for measurement of house dust mite (HDM)-specific IgE.

Blood samples will also be taken at Visit 2 (Day 1) for genotyping to evaluate uridine 5' diphospho-glucuronosyltransferase 1A1 (UGT1A1) and filaggrin polymorphisms to enable pharmacogenomic analyses.

3.4.4 Safety Variables

Safety evaluations, including adverse events (AEs), concomitant medications, medical history, vital signs, physical examinations, standard 12-lead electrocardiograms (ECGs), and laboratory evaluations of safety will be performed as indicated in the Schedule of Assessments (Appendix A) of the clinical study protocol.

3.4.4.1 Adverse Events

An AE is defined as any untoward medical occurrence in a subject administered a pharmaceutical product and which does not necessarily have a causal relationship with this treatment. An AE can therefore be any unfavorable or unintended sign (including a clinically significant abnormal laboratory finding), symptom, or disease temporally associated with the use of a medicinal (investigational) product.

Medical conditions present at baseline that worsen in severity or frequency after exposure to study drug are considered treatment-emergent adverse events (TEAEs). A TEAE is any condition that was not present prior to treatment with the study drug but appeared following treatment, was present at treatment initiation but worsened during treatment, or was present at treatment initiation but resolved and then reappeared while the individual was on treatment (regardless of the intensity of the AE when the treatment was initiated). Planned hospital admissions or surgical procedures for an

illness or a disease that existed before administration of study drug, and for which the condition has not worsened since starting study drug, are not to be considered TEAEs/treatment-emergent serious AEs. Events with emergency room visits that are less than 24 hours will also not be considered SAEs unless they meet one of the criteria listed in Section 11.2.1 of the clinical study protocol.

Abnormal laboratory tests, 12-lead ECG assessments, or vital sign results may constitute an AE if they meet one of the criteria listed in Section 11.1.4.1 of the clinical study protocol. However, whenever possible, the underlying diagnosis should be listed in lieu of associated abnormal results.

Subjects will be assessed for potential drug-induced liver injury (DILI) during the study, although there was no evidence of hepatotoxicity in previous studies related to EP262. Monitoring, interruption, and stopping rules based on multiples of the upper limit of normal (ULN) of aspartate aminotransferase (AST), alanine aminotransferase (ALT), and total bilirubin values are described in section 11.10.3 of the clinical study protocol.

AEs are graded for severity (i.e., intensity) using Common Terminology Criteria for Adverse Events (CTCAE), version 5.0 ([HHS 2017](#)). A severity category of mild, moderate, severe, life-threatening, or death, as defined in Appendix B of the clinical study protocol, will be entered on the AE Electronic Case Report Form (eCRF).

Additional considerations are made for TEAEs falling under certain system organ classes. The study drug must be discontinued for the following TEAEs and CTCAE grades:

- CTCAE Grade 2 or higher in the Cardiac Disorders system organ class
- CTCAE Grade 2 or higher in terms of Bone marrow hypocellular, lymphocyte count decreased, lymphocyte count increased, or myelodysplastic syndrome
- CTCAE Grade 3 or higher in other system organ classes

3.4.4.2 *Laboratory Parameters*

Samples for the following laboratory tests should be collected after an overnight fast (at least 8 hours):

- Chemistry: sodium, albumin, alkaline phosphatase (ALP), bicarbonate, calcium, corrected calcium, chloride, bilirubin (total, indirect, and direct), AST, ALT, blood urea nitrogen, urea, creatinine, glucose, magnesium, phosphorus, potassium, creatine phosphokinase, total cholesterol, triglycerides, high-density lipoprotein cholesterol, low-density lipoprotein cholesterol, lactate dehydrogenase, gamma-glutamyl transferase, and total protein
- Hematology: hemoglobin, hematocrit, mean corpuscular hemoglobin, mean corpuscular hemoglobin concentration, mean corpuscular volume, white blood cell count (total and differential), red blood cell count, platelet count, and platelet volume

- Urinalysis: leukocyte esterase, nitrites, pH, protein, specific gravity, glucose, occult blood, ketones, bilirubin, and urobilinogen; microscopic analysis is to be performed only if protein, leukocyte esterase, blood or nitrite is positive
- Coagulation: activated partial thromboplastin time, international normalized ratio (INR), and prothrombin time
- Pregnancy testing: required for all females; serum test at Screening (Visit 1) and urine test for all other visits where pregnancy testing is required

The urine pregnancy test for female subjects will be conducted locally; all other planned laboratory evaluations of safety will be conducted at a central laboratory. Details for sample collection, processing, storage, and shipment will be provided in the Laboratory Manual.

3.4.4.3 *Other Laboratory Evaluations*

Samples for the following laboratory tests will be collected:

- Serology: HIV I/II, HBV (hepatitis B surface antigen), HCV

These planned laboratory evaluations will be conducted at a central laboratory. See the Laboratory Manual for additional details.

3.4.4.4 *Medical History*

The Investigator or designee will collect and review the subject's medical history, including AD disease history, to evaluate the subject's eligibility for study participation. The new onset of signs, symptoms, or other findings that occur from before signing of the informed consent form (ICF) will be captured as medical history.

3.4.4.5 *Vital Signs*

Vital signs, including sitting systolic and diastolic blood pressure, pulse rate, body temperature, and respiratory rate, will be measured pre-dose (as applicable) after at least 5 minutes of rest. Vital signs are to be performed pre-dose if the dose is administered at the site.

3.4.4.6 *Body Weight and Height*

Body weight should be measured with no shoes and heavy clothing (outdoor clothing such as coats) on and using a calibrated scale throughout the study. Height should be measured using a stadiometer with no shoes.

3.4.4.7 *Physical Examinations*

Physical examinations will include but are not limited to an assessment of general appearance, skin, HEENT (head, eyes, ears, nose, throat), musculoskeletal, thyroid/endocrine, cardiovascular, chest/lung, neurologic, abdomen, and extremities/general body systems.

Abbreviated, symptom-directed physical examinations to assess clinically significant changes from Screening or any new signs or symptoms will be conducted at Visit 3 (Week 3), Visit 5 (Week 10), and the Early Treatment Termination Visit, and may be conducted at other visits as determined by the Investigator based on subject complaint.

Clinically significant abnormalities from before signing of the ICF will be recorded as medical history, and clinically significant changes after signing the ICF will be recorded as AEs.

3.4.4.8 12-Lead Electrocardiograms

Twelve-lead ECGs are to be performed pre-dose (as applicable) with subjects in a supine position after at least 5 minutes of rest. An ECG is to be performed pre-dose if the dose is administered at the site.

3.5 Data Quality Assurance

Report summaries will be generated using validated Base SAS[®] software, version 9.4 or higher, on a PC or server-based platform. Additional validated software may be used to generate analyses, as needed.

All SAS programs that create outputs or supporting analysis datasets will be validated by a second statistical programmer or biostatistician. At a minimum, validation of programs will consist of a review of the program log, review of output or dataset format and structure, and independent confirmatory programming to verify output results or dataset content. Additionally, all outputs will undergo a review by a senior level team member before finalization.

The content of the source data will be reviewed on an ongoing basis by project statistical programmers and statisticians. Data will be checked for missing values, invalid records, and extreme outliers through defensive programming applications, analysis-based edit checks, and other programmatic testing procedures. All findings will be forwarded to the project data manager for appropriate action and resolution.

4. STATISTICAL METHODS

4.1 General Methodology

Data will be analyzed by Emanate biostatistics personnel. Statistical analyses will be reported with tables and listings, presented in rich text format, and using recommended ICH numbering. Output specifications for all tables and listings will be in conformance with guidelines specified by the ICH in Appendix 7 of the Electronic Common Technical Document Specification (Apr 2003).

4.1.1 Reporting Conventions

Tables will be summarized by treatment group. All tables, exclusive of PD and pharmacokinetic (PK) analyses, will also include a column for all subjects combined. In general, all data collected and any derived data will be presented in subject data listings, for all enrolled subjects. Listings will be ordered by subject number, treatment

group, and assessment or event date. The treatment group presented in listings will be based on the planned assignment, unless otherwise noted.

In general, continuous variables will be summarized to indicate the study population sample size (N), number of subjects with available data (n), mean, SD, SE, median, first (Q1) and third (Q3) quartiles, minimum, and maximum values. Categorical variables will be summarized by the population size (N), number of subjects with available data (n), number of subjects in each category, and the percentage of subjects in each category. Unless otherwise noted, the denominator to determine the percentage of subjects in each category will be based on the number of subjects with available data. Select ordinal data may be summarized using both descriptive statistics and counts and percentages of subjects in each category, as appropriate.

Non-zero percentages will be rounded to one decimal place. Rounding conventions for presentation of summary statistics will be based on the precision of the variable of summarization, as it is collected in its rawest form (i.e., on the eCRF or as provided within an external file) and are outlined as follows:

- The mean and median will be rounded to one more decimal place than the precision of the variable of summarization;
- Measures of variability (e.g., SD, SE) will be rounded to two more decimal places than the precision of the variable of summarization; and
- Minimum and maximum values will be presented using the same precision as the variable of summarization.

Other statistics (e.g., CIs) will be presented using the same general rules outlined above, or assessed for the most appropriate presentation based on the underlying data.

No formal statistical analysis will be performed to compare treatment groups. This study is exploratory in nature; descriptive statistics will be tabulated by treatment group and reviewed to evaluate all study endpoints. Any p-values presented are to be considered nominal in their evaluation and interpretation. P-values will be reported for statistical tests, rounded to four decimal places. P-values less than 0.0001 will be displayed as “<0.0001”; p-values greater than 0.9999 will be displayed as “>0.9999”.

4.1.2 Summarization by Visit

Data summarized by study visit will be based on the nominal, scheduled visit label as reported on the eCRF.

Whenever possible, subjects should remain in the study and complete the remaining study visits and assessments even when study drug has been discontinued. Subjects who discontinue study drug for any reason and continue with the study visits as planned through Visit 4 (Week 6) (participating only in PD and safety, but not PK measures) will participate in the Follow-Up Visit if the last dose of study drug was administered less than 4 weeks before Visit 4 (Week 6) to ensure that at least 4 weeks of follow-up data are collected for all randomized subjects. Subjects that discontinue treatments early and complete the remaining study visits will be summarized according to their planned treatment group, unless otherwise noted.

If a subject discontinues study drug and chooses not to complete all of the remaining study visits, the subject should have the Early Treatment Termination visit conducted as soon as possible after the last dose of study drug, ideally within 2 days after the last dose of study drug, and a Follow-Up Visit approximately 4 weeks (± 3 days) after the last dose of study drug if at least 4 weeks of follow-up data have not already been collected. The Early Treatment Termination visit will be mapped and summarized with the next treatment scheduled nominal visit, according to the schedule of events, based on the last visit completed per protocol if the Early Treatment Termination visit falls within the study day visit window defined for that nominal visit.

Data collected at unscheduled visits will not be included in by-visit summaries, but will be considered when endpoint derivations potentially include multiple visits (e.g., determination of baseline value, determination of worst post-baseline value, etc.). All data will be included in subject listings.

4.1.3 Data Handling Rules

Unless otherwise noted, values reported as greater than or less than some quantifiable limit (e.g., " < 1.0 ") will be summarized with the sign suppressed in summary tables, using the numeric value reported. Data will display on subject listings to include the sign.

4.1.4 Standard Calculations

Where appropriate, the calculated study day of each assessment or event will be presented with the assessment or event date on subject data listings, where study day will be determined as:

- The assessment/event date minus the date of first dose of study drug, if the assessment/event date is prior to the date of first dose; and
- The assessment/event date minus the date of first dose of study drug, plus one, if the assessment/event date is on or after the date of first dose.

Other variables requiring calculations will be derived using the following formulas:

- **Days:** A duration between two dates expressed in days will be calculated using the following conventions:
 - Later date – earlier date + 1, if the earlier date is on or after the reference date of interest (e.g., date of first dose of study drug); or
 - Later date – earlier date, if the earlier date is prior to the reference date of interest.
- **Months:** A duration expressed in months will be calculated by dividing the duration in days by $(365.25 / 12)$.
- **Years:** A duration expressed in years will be calculated by dividing the duration in days by 365.25.

- **Change from Baseline:** Change from baseline will be calculated as the post baseline value minus the baseline value.
- **Percentage Change from Baseline:** Percentage change from baseline will be calculated as the change from baseline divided by the baseline value, multiplied by 100.
- **Geometric CV:** calculated as $100 \cdot \sqrt{\exp(\sigma^2) - 1}$, where σ^2 is the variance of the log-transformed data.
- **Log2 Fold Change:** calculated as $B - A$, where: B is the value of interest and A is the value of reference, where B and A are log scale base 2 transformed.

4.2 Analysis Sets

The analysis sets are defined as follows:

- **Full Analysis Set:** All subjects who are randomized and take at least 1 dose of randomized study drug will be included in the Full Analysis Set (FAS). Subjects in the FAS will be analyzed according to randomized treatment assignment. All PD analyses will be based on the FAS.
- **Per Protocol Set:** The Per Protocol (PP) Set is a subset of the FAS containing subjects who meet study eligibility requirements and had no protocol deviations that might impact the assessment of PD measurements. Subjects will be analyzed according to randomized treatment assignment. The PP Set will be used for sensitivity analyses relating to PD. Protocol deviations that qualify for exclusion from the PP Set include:
 - Deviations of inclusion/exclusion criteria
 - Non-permitted concomitant medications or procedures that may meaningfully impact PD outcomes
 - Meaningful dosing and/or randomization error(s)
 - Any other important protocol deviation deemed by the Sponsor to warrant exclusion from the PP set

Any protocol deviations that govern exclusion from the PP Set will be determined prior to database lock.

- **Safety Analysis Set:** All subjects who are randomized and take at least 1 dose of randomized study drug will be included in the Safety Analysis Set. Safety analyses will be based upon treatment actually received.
- **PK Set:** All subjects who receive at least 1 dose of EP262 and provide adequate blood samples for bioanalysis will be included in the PK Set.

Data summaries to be presented on both the Safety Analysis Set and the FAS will only be produced on both analysis sets if there is a difference in the population groups.

4.3 Study Subjects

4.3.1 Disposition of Subjects

Subject disposition will be summarized for all randomized subjects by treatment group and overall subjects combined. Summaries will include the number and percentage of subjects in each analysis set, completing the study, and discontinuing the study early by the primary reason for discontinuation. Subject disposition will also be summarized separately for each study site for all randomized subjects.

The number and percentage of screen failures will be presented based on the total number of subjects screened. The reason for screen failure will also be summarized for screen failures. Screen failures will also be presented in a subject-level listing.

4.3.2 Protocol Deviations

Important Protocol Deviations (IPDs) will be summarized by treatment group and overall subjects combined for the FAS. Important Protocol Deviations are identified by the Sponsor and are defined in the ICH guideline *Structure and Content of Clinical Study Reports – Questions and Answers (E3[R1], 2013)* as a subset of protocol deviations that might significantly affect the completeness, accuracy, and/or reliability of the study data or that might significantly affect a subject's rights, safety, or well-being.

All IPDs will be determined and appropriately categorized prior to database lock and prior to breaking the blind of the treatment group assignments. The number and percentage of subjects with any IPDs as well as the number and percentage of subjects with IPDs within each category will be presented. A listing of important protocol deviations will be provided.

4.4 Statistical Evaluation

4.4.1 Datasets Analyzed

All PD summaries will be based on the FAS; select summaries will also be produced on the PP Set. A data listing of subjects excluded from the FAS or PP Set, to include the reason for exclusion, will be presented.

4.4.2 Demographic and Other Baseline Characteristics

Demographic variables including age, sex, ethnicity and race will be summarized by treatment group and overall subjects combined for the Safety Analysis Set, FAS, PP Set, and PK Set.

Age will be summarized using descriptive statistics. Sex, ethnicity, and race will be summarized with the number and percentage of subjects in each parameter category.

Medical history conditions will be mapped to preferred terms and system organ classes using the Medical Dictionary for Regulatory Activities (MedDRA, version 26.0). Frequency counts and percentages to summarize subjects reporting medical history by

[figure not shown]
system organ class and preferred term will be presented for the FAS and summarized by treatment group and overall subjects combined.

[figure not shown]
Baseline disease characteristics to be summarized include baseline total IgE (kU/L), time since AD diagnosis (as reported on the Disease History eCRF), presence of *S. aureus*, history of asthma, allergic rhinitis, HDM allergy, whether or not the subject has had phototherapy for AD, previously taken other AD medications, or has taken any emollients after diagnosis. The number and percentage of subjects with a baseline total IgE greater than 100 kU/L will also be summarized. Time since AD diagnosis (in years) is calculated as the informed consent date – the date of diagnosis divided by 365.25. Subjects with partial dates reported for the date of diagnosis will have time (years) calculated utilizing the available date information reported. Time since AD diagnosis will be summarized using descriptive statistics. Baseline characteristics will be summarized for the Safety Analysis Set, FAS, PP Set, and PK Set by treatment group and overall subjects combined.

[figure not shown]
Prior reported AD therapies will be coded using the World Health Organization (WHO) Drug Global B3, version March 1, 2023. Therapies entered on the Prior AD eCRF will be mapped to Anatomical Therapeutic Chemical (ATC) drug class (level 2) and preferred name. The number and percentage of subjects receiving any therapy will be summarized by treatment group and overall subjects combined in the FAS, as will the number and percentage receiving any therapy by ATC drug class and preferred name. Subjects reporting use of more than one therapy at each level of summarization (any medication received, ATC class, and preferred name) will be counted only once.

[figure not shown]
Baseline characterization data including UGT1A1, filaggrin polymorphisms, and total HDM – specific IgE will be presented in a listing.

4.4.3 Pharmacodynamic Analysis Methods

4.4.4 *Statistical/Analytical Issues*

4.4.4.1 *Adjustments for Covariates*

The ANCOVA model to compare treatment groups for the skin biopsy-derived biomarkers secondary endpoint of skin histology will include a covariate adjustment for the baseline value. All statistical results presented are to be considered nominal in their evaluation and interpretation.

4.4.4.2 *Handling of Dropouts or Missing Data*

No imputations will be performed on missing data; all analyses will be descriptive in nature and based on observed data only. Any responder analysis will be based on the number of subjects reporting data at the visit of interest.

4.4.4.3 *Interim Analyses and Data Monitoring*

No interim analysis will take place for the study.

4.4.4.4 *Multicenter Studies*

This is a multicenter study to be conducted within North America. Pharmacodynamic data collected from all study sites will be pooled for data analysis. The effect of study site on the analysis results may be explored post-hoc, as needed.

4.4.4.5 *Multiple Comparisons/Multiplicity*

[figure not shown]
For analysis of gene expression, the Bonferroni correction will be used to control the alpha at 5%. For analysis of other parameters, there will be no adjustments for multiple comparisons in the analysis for this study. Results are descriptive in nature and there will be no formal comparisons made among treatment groups. All statistical results presented are to be considered nominal in their evaluation and interpretation.

4.4.4.6 *Use of an “Efficacy Subset” of Subjects*

The primary analysis will be performed on the FAS; the PP Set will be utilized as a sensitivity analysis. The PP Set will exclude subjects with IPDs.

4.4.4.7 *Active-Control Studies Intended to Show Equivalence*

This study does not include an active-control product and is not intended to demonstrate equivalence between any two drug products.

Additional subgroup analyses may be performed post-hoc, as appropriate.

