#### 7.1.2. Double-Blind Treatment Period

The Double-Blind Treatment Period will consist of 3 study visits (Visits 2, 3, and 4 [Day 1, Week 3, and Week 6]). During this period, all subjects who meet eligibility requirements will be enrolled into the study and will be randomized on Visit 2 (Day 1), in a 2:1 ratio, to receive double-blind, PO, QD 150 mg doses of EP262 or placebo for 6 weeks. Randomization will be conducted centrally via an Interactive Web Response System (IWRS). QD PO dosing of study drug should occur after at least a 4 hour fast and administered at approximately the same time of day. Subjects should refrain from eating for at least 2 hours postdose. The time and date of all dose administrations will be recorded in a daily diary. The first dose of study drug will be administered at the clinical site on Visit 2 (Day 1) after all baseline study procedures are completed. Visit 2 (Day 1) will not have a visit window; all other visits in the Double-Blind Treatment Period will have a visit window of ±3 days. Subjects who discontinue from treatment early should have the Early Treatment Termination Visit conducted as soon as possible after the last dose of study drug, ideally within 2 days after the last dose of study drug.

<sup>a Any subject who completes the Double-Blind Treatment Period or discontinues study drug (EP262 or placebo) early will have a Follow-Up Visit approximately 4 weeks (±3 days) after the last dose of study drug.

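### Responder rates count only subjects with data at the visit, so a subject whose termination visit falls before Day 40 and who misses Visit 4 leaves the Week 6 denominator, even if worsening AD was the reason (low priority)

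*SAP*

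**What the plan says.** SAP 4.4.4.2 (Handling of Dropouts or Missing Data) sets the rule in two sentences: "No imputations will be performed on missing data; all analyses will be descriptive in nature and based on observed data only", and "Any responder analysis will be based on the number of subjects reporting data at the visit of interest". SAP 4.1.1 has the same default for percentages: unless otherwise noted, "the denominator to determine the percentage of subjects in each category will be based on the number of subjects with available data". The same section has tables show the counts behind the percentage: "Categorical variables will be summarized by the population size (N), number of subjects with available data (n), number of subjects in each category".

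SAP 4.1.2 maps an Early Treatment Termination visit to the next scheduled treatment visit only "if the Early Treatment Termination visit falls within the study day visit window defined for that nominal visit". Data from unscheduled visits stay out of by-visit summaries. Protocol 7.1.2 gives the window: "all other visits in the Double-Blind Treatment Period will have a visit window of ±3 days". Protocol Appendix A puts Visit 3 at Day 22 and Visit 4 at Day 43.

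SAP 3.3.5 has study drug stopped when intolerable AD symptoms need new treatment, and asks such subjects to stay in the study where possible. SAP 4.1.2 also provides for those who do not stay: "If a subject discontinues study drug and chooses not to complete all of the remaining study visits". SAP 4.2 says of the population: "All PD analyses will be based on the FAS".

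**The concern.** Whether a subject is in the Week 6 responder denominator can depend on outcome. Someone whose AD becomes intolerable stops study drug, has a termination visit on, say, Day 30, and declines the remaining visits. Clinically that is a treatment failure. In the responder table the subject is neither a responder nor a non-responder.

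Losing failures raises the printed response rate in the arm that loses them. The between-arm difference then depends on how many failures each arm loses. With about 10 subjects on placebo, one or two such losses are visible in the percentage. Protocol 5.2 includes the clinical scores to look for trends against placebo, so the printed percentages will be read that way.

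No readable analysis checks for this. The one stated sensitivity analysis, on the Per Protocol Set, can exclude subjects who took non-permitted AD treatment, so it may remove more of the same subjects. Rescue users are only listed (SAP 4.5.6.4 and 4.5.6.5).

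**Working it through.** The documents state no responder rate, dropout rate or power, so there is no figure of the plan's own to reproduce. The check covers the windows first and then the possible size.

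**Windows**
- Week 6: 43 − 3 = 40 and 43 + 3 = 46, so Days 40 to 46.
- Week 3: 22 − 3 = 19 and 22 + 3 = 25, so Days 19 to 25.
- A termination visit on Days 26 to 39 maps to no visit. One on Days 2 to 18 also maps to none, so if Visit 3 is missed too the subject is absent at Week 3 as well.
- The cut-off is the date of the termination visit, not of the last dose. That visit is ideally within 2 days of the last dose. A last dose on Day 37 gives a visit by Day 39 (not mapped). A last dose on Day 38 or 39 can give a visit on Day 40 or 41 (mapped to Week 6).

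**Size (illustration)**

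Inputs: about 30 subjects at 2:1 (SAP 3.3.2), so 20 and 10. Responder and loss counts are assumptions, and every lost subject is taken to be a non-responder. The observed-case rate is responders / (arm size − lost). The full-FAS rate is responders / arm size.

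| Full-FAS result | Lost, EP262 / placebo | Observed-case rates | Difference (points) |
|---|---|---|---|
| 8/20 v 2/10 (+20.0) | 2 / 2 | 8/18 v 2/8 = 44.4% v 25.0% | +19.4 |
| | 4 / 2 (20% of each) | 8/16 v 2/8 = 50.0% v 25.0% | +25.0 |
| | up to 10% per arm, lowest (0 / 1) | 8/20 v 2/9 = 40.0% v 22.2% | +17.8 |
| | up to 10% per arm, highest (2 / 0) | 8/18 v 2/10 = 44.4% v 20.0% | +24.4 |
| | up to 20% per arm, lowest (0 / 2) | 8/20 v 2/8 = 40.0% v 25.0% | +15.0 |
| | up to 20% per arm, highest (4 / 0) | 8/16 v 2/10 = 50.0% v 20.0% | +30.0 |
| 6/20 v 3/10 (0.0) | 4 / 2 (20% of each) | 6/16 v 3/8 = 37.5% v 37.5% | 0.0 |
| | up to 10% per arm, lowest (0 / 1) | 6/20 v 3/9 = 30.0% v 33.3% | −3.3 |
| | up to 10% per arm, highest (2 / 0) | 6/18 v 3/10 = 33.3% v 30.0% | +3.3 |
| | up to 20% per arm, lowest (0 / 2) | 6/20 v 3/8 = 30.0% v 37.5% | −7.5 |
| | up to 20% per arm, highest (4 / 0) | 6/16 v 3/10 = 37.5% v 30.0% | +7.5 |

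If the same fraction f of each arm is lost and all are failures, both rates are divided by (1 − f), and so is their difference: 20.0 / 0.8 = 25.0, while 0 / 0.8 = 0. A non-zero difference widens and a zero difference stays zero. Equal counts from unequal arms can narrow it (+19.4 above).

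For scale, the standard error of 40% v 20% at 20 and 10 is √(0.4 × 0.6/20 + 0.2 × 0.8/10) = √0.028 = 0.167, or about 16.7 points.

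**The case against.** The strongest reply is that the affected analysis cannot be seen. The methods under SAP 4.4.3 are not in the public text, and no responder endpoint, definition or visit is readable. The readable assessment list for the termination visit (Protocol 9.4.4) does not show whether severity scores are taken there. A responder measure based on a daily diary, if there is one, might have data without Visit 4. All this stands as a limit. It does not remove the point, because the SAP 4.4.4.2 rule is written to cover any responder analysis.

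The plan also goes some way to meet the concern. Subjects are asked to stay after stopping drug, disposition is tabulated by arm with reasons, rescue users are listed, and N, n and counts let a reader work out responders/N by hand. Results are descriptive and nominal. In the examples every shift is below one standard error, and the extremes need one arm to lose its maximum and the other none. This lowers the priority. The denominator can still depend on outcome, and such a shift comes on top of sampling error.

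Three stronger readings are tempting, and the documents do not support them:
- A reader might infer that the rule contradicts the statement that PD analyses use the FAS. It does not: the FAS defines the population, SAP 4.1.1 separates N from n, and the observed-case denominator is stated openly.
- A reader might infer that the rule favours EP262. The direction is undetermined, and with no true difference the ranges above are symmetric about zero.
- A reader might infer that anyone who stops before Day 40 is lost. Subjects who stop drug but attend Visit 4 are counted, and what matters is the date of the termination visit.

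**Conclusion.** The point holds as a low-priority gap in how responder rates will be reported. A subject with a termination visit before Day 40 who does not attend Visit 4 has no Week 6 visit record and is left out of the Week 6 responder denominator, whatever the reason for leaving. No readable rule or sensitivity analysis shows the effect.

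On the assumed counts, a +20.0-point difference could read +17.8 to +24.4 with up to 10% lost per arm, and +15.0 to +30.0 with up to 20%. This rests on assumed response and loss rates and on every lost subject being a failure. It also requires that a visit-based responder endpoint exists. The primary safety objective and the secondary biopsy endpoint do not depend on it.

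**What to change.** In SAP 4.4.4.2, add one sentence: for any responder endpoint assessed at a treatment-period visit, also report the rate over all FAS subjects in the arm, with missing counted as non-response, as a sensitivity row beside the planned observed-case rate. The Follow-Up Visit can stay observed-case.

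The cost is that sentence and one row per responder table, with no new data. The downside is that dropouts unrelated to AD also count as failures, so rates and differences shrink slightly. With 40% v 20% and 10% of each arm lost for unrelated reasons, the all-FAS rates are 0.40 × 0.9 = 36% and 0.20 × 0.9 = 18%, a difference of +18.0 points instead of +20.0. Printing both rows shows how far the missing data matter.

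The row does not change how subjects who use rescue but stay and are assessed are counted. They keep their observed value.
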